Lacosamide is well-tolerated and has no known drug-drug interactions. In controlled clinical trials, the rate of discontinuation as a result of an adverse event was 8% and 17% in patients randomized to receive lacosamide at the recommended doses of 200 and 400 mg/day, respectively, 29% at 600 mg/day, and 5% in patients randomized to receive placebo. The adverse events most commonly leading to discontinuation were dizziness, ataxia, vomiting, diplopia, nausea, vertigo, and vision blurred. Abnormalities in liver function tests have been observed in controlled trials with lacosamide in adult patients with partial-onset seizures who were taking 1 to 3 concomitant AEDs. Elevations of ALT to $\geq 3 \times$ the upper limit of normal (ULN) occurred in 0.7% (7/935) of lacosamide patients and 0% (0/356) of placebo patients. One case of hepatitis with transaminases $> 20 \times$ ULN was observed in one healthy subject 10 days after lacosamide treatment completion, along

with nephritis (proteinuria and urine casts). Serologic studies were negative for viral hepatitis. Transaminases returned to normal within one month without specific treatment. At the time of this event, bilirubin was normal. The hepatitis/nephritis was interpreted as a delayed hypersensitivity reaction to lacosamide.

A list of possible adverse events is provided in Section 3.12. This includes events reported by patients treated with lacosamide in all clinical trials in patients with partial-onset seizures, including controlled trials and long-term open-label extension trials, as well as events identified during post approval use of lacosamide. Because the latter are reported voluntarily from a population of uncertain size, it is not always possible to reliably estimate their frequency or establish a causal relationship to drug exposure. The most frequently reported adverse events include dizziness, vertigo, diplopia, blurred vision, nystagmus nausea/vomiting, diarrhea, fatigue, headache, somnolence, tremor, ataxia, and imbalance. Post approval adverse events of potential significance include bradycardia and rash.

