There was no evidence of drug related carcinogenicity in mice or rats. Mice and rats received lacosamide once daily by oral administration for 104 weeks at doses producing plasma exposures (AUC) up to approximately 1 and 3 times, respectively, the plasma AUC in humans at the maximum recommended human dose (MRHD) of 400 mg/day. Lacosamide was negative in an *in vitro* Ames test and an *in vivo* mouse micronucleus assay. Lacosamide induced a positive response in the *in vitro* mouse lymphoma assay. No adverse effects on male or female fertility or reproduction were observed in rats at doses producing plasma exposures (AUC) up to approximately 2 times the plasma AUC in humans at the MRHD.

3.12 **Human Toxicity:**

Likely (occurring in more than 20% of patients)

- Dizziness

Common (occurring in 3 – 20% of Patients)

- Vertigo
- Diplopia
- Blurred vision
- Nausea
- Vomiting
- Diarrhea
- Fatigue
- Headache
- Ataxia
- Somnolence
- Tremor
- Nystagmus
- Imbalance (possibly with associated falls)

Rare but Serious (occurring in fewer than 3% of patients)

- Suicidal ideation or behavior
- PR prolongation, first degree AV heart block
- Atrial fibrillation or flutter
- Syncope
- Multi-organ hypersensitivity reactions (also known as Drug Reaction with Eosinophilia and Systemic Symptoms, or DRESS)

3.13 Clinical Pharmacokinetic Properties:

The pharmacokinetics of lacosamide has been studied in healthy adult subjects (age range 18 to 87), adults with partial-onset seizures, adults with diabetic neuropathy, and subjects with renal and hepatic impairment. Lacosamide is completely absorbed after oral administration with negligible first-pass effect with a high absolute bioavailability of approximately 100%. The maximum lacosamide plasma concentrations occur approximately 1 to 4 hours post-dose after oral dosing, and elimination half-life is approximately 13 hours. Steady state plasma concentrations are achieved after 3 days of twice daily repeated administration. Pharmacokinetics of lacosamide are dose proportional (100-800 mg) and time invariant, with low inter- and intra-subject variability. Compared to lacosamide, the major metabolite, O-desmethyl metabolite, has a longer T_{max} (0.5 to 12 hours) and elimination half-life (15-23 hours).

3.14 Administration: Oral.

3.15 Supplier:

Lacosamide is commercially available, but study drug and identical placebo will be supplied by UCB.

3.15.1 Agent Distribution:

Ordering Study Agent/s:

See Section 15.3.2

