11.0 STATISTICAL CONSIDERATIONS

11.1 Overview

The primary analysis for this study is a randomized, two-arm, parallel group, multicenter trial enrolling post-operative patients with newly-diagnosed high-grade glioma (HGG). Patients will be randomly assigned to either lacosamide (L) or placebo (P). Patients will be randomized to either treatment using a 1:1 randomization scheme. Based on a retrospective review of available data we assume a 20% seizure risk in the P group and 8% in the L group (after 1 year of observation). Based on these assumptions and assuming that time to first seizure follows an exponential distribution we estimate the hazard ratio between the L and P arms to be 0.374. Additional assumptions of the trial are that patients will be administratively censored after 1 year of follow-up and that 15% of patients will be lost to follow-up. The reason for the first assumption is that risk of seizure is greatest during the first year and as such clinical interest focuses on this time period. Because standard software packages do not incorporate administrative censoring we developed a SAS IML program to estimate the power associated with this clinical trial design.

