Based on this simulation program, the maximum fixed sample size to be accrued is 298 patients. The power for this analysis is 83.6% (power based on 1000 simulations). Because we plan 1 interim analysis using an O'Brien-Fleming stopping rule, we will need to adjust the sample size upward using the group sequential-to-fixed sample size ratio of 1.008 [35]. While this ratio is exact for trials with 80% power, it is a conservative lower bound for trials with greater than 80% power [35]. This ratio results in a trial with 302 patients (i.e., the largest even integer greater than 298×1.008). This results in a trial with 151 patients randomized to L and 151 patients randomized to P. The primary measure of efficacy is time to first seizure (TFS). The primary test of the difference in TFS between the treatment arms will be based on the likelihood ratio statistic for the treatment effect in a stratified proportional hazards regression model with anticonvulsant use as the stratification factor. The MDACC DSMB will periodically meet (either once every 6 months or annually) to evaluate safety and efficacy. The interim analysis will take place after 21 events have been observed. We will assess efficacy using an O'Brien-Fleming stopping rule with a nominal critical value of 2.7959 at the interim analysis. A futility analysis based on a conditional power assessment may be performed if the hazard ratio between the two treatment arms is approximately 1. If a conditional power assessment is performed and the conditional power is less than 0.10 the trial will be stopped for futility. The decision to perform this futility analysis will include an assessment of the number of events observed (i.e., at least 50% of the expected 42 events have occurred and all patients have not yet enrolled in the trial). If the study continues to full accrual, the final analysis will take place when all of the patients have either been followed for 1 year or have experienced a seizure event. We will test the null hypothesis $HR=1.00$ against $HR \neq 1.00$ at the 0.05 level. The conditional power for the time-to-event outcome will be computed based on the method described in Design and Analysis of Clinical Trials with Time-to-Event Endpoints (Peace 2009, page 60) and Lan Simon and Halperin (1982).

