Descriptive and inferential statistics will be used to summarize the treatment effects. The mean, standard deviation, median, 25% percentile, 75% percentile, minimum, and maximum will be reported for continuous variables by treatment group. For discrete (qualitative) outcomes, descriptive analyses will be based on the distribution of these discrete outcomes and will be reported as percentages and patient counts by treatment. Time to event endpoints will be descriptively summarized by Kaplan-Meier curves. Point and interval estimates of treatment effects will be based on maximum likelihood methods. For binomially distributed variables, we will report proportions, their 95% confidence intervals, differences in proportions and 95%

confidence intervals for the difference in proportions. Estimates of treatment effects for time to event endpoints will be based on the ratio of hazard functions (L: P) using Wald type scores from a Cox proportional hazards regression model. Unless stated otherwise, all statistical tests will be assessed using a two-sided $\alpha = 0.05$ significance level and confidence intervals will be constructed using two-sided 95% and will be based on the normal approximation. Although multiple secondary endpoints will be evaluated we will make no adjustment for multiplicities associated with these multiple tests.

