11.2.5 Adverse Events

Clinical and laboratory adverse events will be coded using the NCI's Common Terminology Criteria for Adverse Events (CTCAEv4.0). The CTCAEv4.0 will be attached to the clinical database.

Summaries of unique adverse events will include

- all treatment emergent adverse events,
- all treatment emergent adverse events by the worst grade,
- all related treatment emergent adverse events,
- all related treatment emergent adverse events by the worst grade,
- all adverse events leading to study drug discontinuation

Treatment emergent adverse events are

- Events with onset dates on or after the start of treatment and up to 30 days after the permanent discontinuation of the study medication
- Continuing adverse events diagnosed before the start of treatment and getting worse in grade or relationship to treatment after the start of treatment.

Related adverse events include all those classified by the investigator as definitely, probably, or possibly related to the study drugs. Events for which the investigator did not record relationship to study drug will be considered related to study drug.

Multiple events will be counted once only per patient in each summary. In the presentation, Adverse Event Categories will be sorted in alphabetical order. Within Categories adverse events will be sorted in descending order of total events. For summaries by severity, the most severe event will be selected.

Deaths and serious adverse events

Serious adverse events and deaths will be listed. Data from the adverse event page that specify the event is serious will be used to generate the listing.

Summaries of serious unique adverse events will include:

- all serious treatment emergent adverse events,
- all related serious treatment emergent adverse events by the worst grade,

11.3 Patient Reported Outcomes.

The sample size for this trial was based on the primary endpoint of the study.

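### Section 11.2.5 pre-specifies no pooled group for the cardiac harms that 3.12 lists at under 3% each, so its tables have little chance of showing an excess

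*Combined protocol and SAP*

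**What the plan says.** Section 3.12 (Human Toxicity) sorts the expected harms of lacosamide into three frequency bands. Dizziness is above 20%. Vertigo, ataxia, imbalance, nystagmus, tremor, diplopia and blurred vision are at 3-20%. Suicidality, PR prolongation or first-degree AV block, atrial fibrillation or flutter, syncope and multi-organ hypersensitivity come under "Rare but Serious (occurring in fewer than 3% of patients".

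Section 2.5 points to that list ("A list of possible adverse events is provided in Section 3.12") and says it covers events identified after approval. The same section then adds: "Post approval adverse events of potential significance include bradycardia and rash". It also reports ALT elevations of at least 3 times the upper limit of normal in 0.7% of lacosamide patients and 0% on placebo. Bradycardia, rash and ALT elevation do not appear in 3.12.

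Section 11.2.5 codes events by CTCAE v4.0 and plans general summaries: treatment-emergent, related, worst grade, leading to discontinuation, and serious. On layout it says: "In the presentation, Adverse Event Categories will be sorted in alphabetical order". Terms are then ordered by frequency within category, and a patient counts once per summary. It names no event of special interest, no pooled term list and no group comparison. It does not say whether a per-patient total is shown for each category.

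**The concern.** The drug is given to prevent a first seizure in patients without recent seizures, so the trial's conclusion depends on weighing benefit against harm. The protocol already treats conduction and rhythm effects as known risks: 2.5 describes them, and 4.15 and 4.16 exclude patients with heart block, arrhythmia or a PR interval above 200 ms. If a true cardiac excess is spread over several rare terms, each row of the table holds a handful of patients and none need look unusual. A group chosen after unblinding could be assembled to fit the data and would carry little weight. The group therefore has to be named beforehand.

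**Working it through.** **1. The plan's own figures.** The documents give no power or precision for any adverse event, so only the design inputs can be checked. The hazard ratio is ln(0.92)/ln(0.80) = 0.374, as 11.1 states. A log-rank simulation with 298 patients, 1-year censoring and 15% exponential loss gives 83.5% power, against the stated 83.6%. 298 × 1.008 = 300.4, and the next even integer that also splits equally with a whole number per arm as planned is 302: "This results in a trial with 151 patients randomized to L and 151 patients randomized to P".

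**2. Inputs.** 151 per arm and two-sided 0.05 (11.1); lacosamide frequency bands (3.12). Placebo rates are assumptions: 0.7-1% per cardiac term, and 5-12% for dizziness. A fourth cardiac term, bradycardia, is taken from 2.5, which gives no frequency; it is assumed to match the others.

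**3. Group rates.** Four independent terms at 3% v 1% give 1 − 0.97⁴ = 11.5% v 1 − 0.99⁴ = 3.9%. Four at 2% v 0.7% would give 7.8% v 2.8% if independent; 6% v 2% allows for patients who have more than one of the events.

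**4. Power.** Binomial probabilities are summed over all pairs of counts that give p ≤ 0.05.

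| Lacosamide v placebo | Expected patients | Fisher | z test |
|---|---|---|---|
| One cardiac term, 2% v 0.7% | 3.0 v 1.1 | 3% | 14% |
| One cardiac term, 3% v 1% | 4.5 v 1.5 | 10% | 22% |
| Cardiac group, 6% v 2% | 9.1 v 3.0 | 31% | 43% |
| Cardiac group, 11.5% v 3.9% | 17.4 v 5.9 | 64% | 71% |
| Dizziness, 20% v 5% | 30.2 v 7.6 | 98% | 99% |
| Dizziness, 20% v 8% | 30.2 v 12.1 | 83% | 86% |
| Dizziness, 20% v 10% | 30.2 v 15.1 | 63% | 69% |
| Dizziness, 20% v 12% | 30.2 v 18.1 | 42% | 48% |

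For a single rare term, Fisher's test needs a split of at least 6 v 0, 8 v 1 or 10 v 2. The expected 3.0-4.5 patients on lacosamide seldom reach that.

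**5. Sensitivity (Fisher).** With only the three cardiac items in 3.12 and no overlap, the group has 78% at 8.7% v 1.5%, 47% at 8.7% v 3%, and 15% at 6% v 3%. Without PR prolongation it has 53% at 5.8% v 1% and 28% at 5.8% v 2%. With 128 per arm (151 × 0.85), one term at 2.9% v 1% has 6% and the group at 8.7% v 3% has 38%.

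**6. Precision.** The half-width is 1.96 × √[p₁(1−p₁)/151 + p₀(1−p₀)/151]. One term at 3% v 1% gives a difference of 2.0 ± 3.1 percentage points. The group at 6% v 2% gives 4.0 ± 4.4, and at 11.5% v 3.9% it gives 7.6 ± 6.0.

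**The case against.** **Events are not confined to single terms.** A reader might infer that 11.2.5 reports single terms only and never groups them. The text does not say that. Tables are arranged by category and patients are counted once per summary, so category counts are neither promised nor excluded. This stands. But a category total is a general coding class, not a set of terms drawn from 3.12.

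**Balance harm would show.** A reader might extend the point to balance and coordination. Section 3.12 does not support that: dizziness is above 20% and the related terms run from 3% to 20%. At 20%, dizziness alone has 63-98% power (Fisher) against 5-10% on placebo. This stands.

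**The plan is descriptive.** Testing four terms separately would carry 1 − 0.95⁴, about 19%, false positives. That is beside the point, because 11.2.5 prescribes no term-by-term tests. Power here only measures how visible an excess would be; the intervals in step 6 lead to the same conclusion.

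**Other safeguards exist.** Serious events and deaths are listed, discontinuations are summarised, the DSMB reviews safety, and the MDASI-BT is collected every 4 weeks. Section 11.1 promises differences with 95% CIs for binomial variables. These help, but a listing gives no between-arm estimate, and the 11.1 promise reaches a group only once the group is defined.

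**Pooling cannot recover what is not recorded.** EKG and laboratory tests are routine only at baseline (6.2.1.1, 8.1, Figure 8-1), and 15.6 counts a test result as an event only if it causes symptoms or needs therapy. Silent PR prolongation and ALT rises will be under-recorded however the tables are arranged. This stands and limits the gain.

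**Conclusion.** The point holds for cardiac harm. No pooled group is pre-specified, and with rates under 3% per term an excess would most likely not be visible term by term: about 3-10% power by Fisher, against 31-64% for a pooled group. These figures rest on assumed placebo rates, on an assumed rate for bradycardia, and on the 3.12 bands carrying over to this population. Under less favourable assumptions the pooled group falls to 15%, so pooling improves the chance of seeing an excess without assuring it.

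The documents do not support the wider conclusion that all the expected toxicities would go unseen. The mismatch between 2.5 and 3.12 is real but clerical. Overall this is a moderate reporting gap.

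**What to change.** In 11.2.5, pre-specify with term lists:

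- a cardiac rhythm and conduction group, including bradycardia and syncope;
- as secondary groups: balance, coordination and vision with falls; suicidality; and hypersensitivity, rash and liver.

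For each group, report patients with at least one event by arm and the risk difference with 95% CI. Keep the single-term tables, and state whether category totals are shown. Note beside the cardiac and liver results that asymptomatic PR and ALT changes are under-recorded by design. Reconcile 3.12 with 2.5 on bradycardia, rash and ALT elevation.

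The cost is a paragraph of SAP wording and one or two tables from events already coded. The downside is that a group pools events of unequal severity, which is why the single-term tables should stay.

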4.0 ELIGIBILITY CRITERIA

This study was designed to include women and minorities, but was not designed to measure differences of intervention effects. Males and females will be recruited with no preference to gender. No exclusion to this study will be based on race. Minorities will actively be recruited to participate.

Unless otherwise specified in the Inclusion Criteria, all patients must meet the General Eligibility Criteria described below.

All patients who meet the following eligibility criteria must be registered with the Brain Tumor Trials Collaborative via the Office of Multicenter Clinical Research (MDACC OMCR) at the University of Texas, MD Anderson Cancer Center (UT MDACC) prior to starting treatment. The OMCR's registration procedures are described in the Multicenter Procedures section of this protocol. **Patients must initiate study treatment within 14 days after registration.**

General Inclusion Criteria

- 4.1 Patients with histologically confirmed supratentorial high-grade glioma will be eligible for this protocol.
- 4.2 All patients must sign an informed consent indicating that they are aware of the investigational nature of this study.
- 4.3 Patients must have signed an authorization for the release of their protected health information.
- 4.4 Patients must be ≥ 18 years old.
- 4.5 Patients must have a Karnofsky performance status of ≥ 60 .
- 4.6 Women of childbearing potential must have a negative β -HCG pregnancy test documented within 2 weeks prior to registration.
- 4.7 In the opinion of the treating investigator, patients must have adequate cognitive abilities to complete the neurocognitive components of the study.
- 4.8 Patients must be able to safely swallow pills.
- 4.9 Patients must agree to practice adequate contraception.
- 4.10 Patients must be registered on study within 16 weeks after the surgical procedure that established the diagnosis of High Grade Glioma.

General Exclusion Criteria

- 4.11 Patients must not have any significant medical or psychiatric illnesses that in the investigator's opinion cannot be adequately controlled with appropriate therapy or would compromise the patient's ability to tolerate this therapy.
- 4.12 Patients must not have serious intercurrent medical illness. Serious, active co-morbidity, defined as follows:

- Unstable angina and/or congestive heart failure requiring hospitalization within the last 12 months.
 - Transmural myocardial infarction within the last 6 months.
 - Acute bacterial or fungal infection requiring intravenous antibiotics at the time of registration.
 - Chronic Obstructive Pulmonary Disease exacerbation or other respiratory illness requiring hospitalization or precluding study therapy at the time of registration.
 - Hepatic insufficiency resulting in clinical jaundice and/or coagulation defects; note, however, that laboratory tests for liver function and coagulation parameters are not required for entry into this protocol.
 - Acquired Immune Deficiency Syndrome (AIDS) based upon current CDC definition; note, however, that HIV testing is not required for entry into this protocol. The need to exclude patients with AIDS from this protocol is necessary because the treatments involved in this protocol may be significantly immunosuppressive.
 - Active connective tissue disorders, such as lupus or scleroderma, which in the opinion of the treating physician, may put the patient at high risk for radiation toxicity.
- 4.13 Patients must not be pregnant or breast feeding Patients must not be pregnant because lacosamide produced developmental toxicity in rats following administration during pregnancy. There is insufficient information to determine if lacosamide is safe during lactation.
- 4.14 Patients must not have any disease that will obscure toxicity or dangerously alter, Drug metabolism
- 4.15 Patients must not have a history of heart block or cardiac arrhythmia, including asymptomatic arrhythmias and atrial fibrillation/flutter.
- 4.16 Patients must not have a prolonged PR interval (defined as > 200 ms).
- 4.17 Perioperative anticonvulsants should be tapered as indicated in section [6.2.1.4](#)
- 4.18 Patients must not have a history of any type of seizure for at least 10 years prior to registration.

5.0 STRATIFICATION/DESCRIPTIVE FACTORS

For the purposes of statistical analysis, patients will be stratified based on use or non-use of peri-operative AEDs and by institution

6.0 TREATMENT PLAN

6.1 General

All patients who meet eligibility criteria must be registered with the Brain Tumor Trials Collaborative Office of Multicenter Clinical Research (MD Anderson OMCR) at the University of Texas, MD Anderson Cancer Center (UT MD Anderson). Patients must initiate study treatment within 14 days after registration. All patients will be monitored for clinical evidence of toxicity as described in section 8.0.

